## REVISION HISTORY

Revision #	Version Date	Summary of Changes
V. 2	5-11-20	Misc. details for IRB submission
V. 3	6-9-20	Clarification regarding the use of verbal consenting, clarification regarding subject recruitment, changes to participant compensation, updated version and date, added study team info
V.4	8-17-21	Addition of opt-in portion of the study involving blood sample to coincide with assessment time points

## 1.0 Study Summary

Study Title	Building Adaptive Coping and Knowledge to Improve Daily Life (Back2Life): A Pilot Feasibility Clinical Trial for Youth with Chronic Sickle Cell Pain
Study Design	Single-Arm, Uncontrolled Behavioral Clinical Trial
Primary Objective	Conduct a pilot proof-of-concept clinical trial to evaluate the feasibility, acceptability, and preliminary efficacy of Back2Life with youth with chronic SCD pain and their parents
Secondary Objective(s)	Refine intervention content and delivery based on participant qualitative feedback; Evaluate a biological response to intervention
Research Intervention(s)/Interactions	The treatment program includes 6-sessions of standard cognitive-behavioral therapy (CBT) treatment (delivered to all participants) and 1-4 tailored sessions to address common co-morbidities associated with chronic pain (sessions assigned based on results of baseline assessment). The treatment manual leverages existing evidence-based interventions into a treatment package that will be tailored to individual patient and family needs.
Study Population	Children with sickle cell disease (SCD) aged 10-18 years old and their parent(s)
Sample Size	25 parent-child dyads
Study Duration for individual participants	8 months
Study Specific Abbreviations/ Definitions	Back2Life: Building Adaptive Coping and Knowledge To improve daily Life CBT: cognitive-behavioral therapy
Funding Source (if any)	NHLBI

## 2.0 Objectives\*

**2.1 Primary Aim:** Conduct a pilot proof-of-concept clinical trial to evaluate the feasibility, acceptability, and preliminary efficacy of Back2Life with youth with chronic SCD pain and their parents (n=25). We will use an adaptive treatment approach with 6-10 module-based treatment sessions selected on the

basis of baseline assessment (rather than a fixed treatment approach) to allow flexibility in tailoring treatment components to meet individual family needs.

*2.2 Hypothesis 1: It is expected that the Back2Life treatment program will be feasible and acceptable as demonstrated by high levels of treatment engagement ( $\geq 80\%$  attendance of treatment sessions) and high ratings of treatment satisfaction.*

*2.3 Hypothesis 2: Participants who complete the Back2Life treatment program will report reductions in pain interference and pain symptoms (intensity and frequency) at post-treatment and 6-month follow-up. Preliminary efficacy will be defined as clinically significant ( $\geq 30\%$ ) reductions in pain interference and pain.*

*2.4 Exploratory hypothesis 1: We will explore reductions in secondary outcomes related to healthcare use for pain (inpatient hospitalizations, ED visits, and opioid use) at 6-month follow-up.*

*2.5 Exploratory hypothesis 2: The Back2Life treatment program will result in measurable reductions in inflammatory biomarkers from baseline to 3-month and 6-month follow-up.*

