**6.5 Follow-Up Assessments:** All teens and parents will complete the same assessment of surveys after completing the standard 6-session program (post-treatment evaluation). Parents will also report on any changes to their teen's medical treatment plan since the last assessment. All teens and parents will

*complete the assessments at 3-months and 6-months follow-up from baseline. All assessments can be completed in-person, at home using online or paper-and-pencil questionnaires, or by telehealth (video or phone) depending on teen and parent preference. An assessment window of +/- 2 weeks will allow flexibility to support recruitment and adherence.*

**6.6 Blood Sample Collection:** *As an optional component of the study, all teens will have the option to consent to blood sample collection at three assessment visits: baseline, 3-month follow, and 6-month follow-up. Blood sample collection will occur at or close to each time point allowing at least 2 weeks following an acute care visit for pain to ensure steady disease state collection. To enhance clinical implementation and acceptability, efforts will be made to coordinate blood sample collection during routine medical visits to minimize blood draws. Each sample will be about 4 teaspoons (about 20 milliliters) of blood, which will be drawn in the clinic or hospital, and will only take a few seconds. Collected blood samples will be immediately transported to [name] laboratory for labeling, processing, storage, and analysis.*

**6.7 Qualitative Interview:** *At the end of the treatment program, parents and teens will be asked for feedback in a one-on-one interview lasting about 30 minutes. Feedback may include how they liked the program, what they thought about the content of the program, and any suggestions or changes to the materials or format. Information from these interviews will be used to refine and modify the Back2Life program. Interviews can be conducted in-person or by telehealth (video and/or phone). Interviews will be audio recorded as digital files and transcribed for analysis by advanced psychology PhD students or trained study members. Audio recordings will be saved for up to 6 years following completion of the study and saved via password-protected computer that is only accessible to the PI to ensure security. No audio recordings will be used for educational or presentation purposes. The research design does not require subjects to be deceived.*

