## **14.0 Withdrawal of Participants\***

- 14.1** Participants have the right to leave the study at any time without penalty. If participants choose to go off the study treatment or leave the study before the final planned study visit, participants may be asked to have some final study procedures completed including but not limited to follow-up surveys at the planned end of the program, and follow-up surveys at 3-months and 6-months after the program.
- 14.2** Study personnel may stop participant involvement in the study without participant consent for any reason to maintain the best interest of the participant or if participants object to any future changes that may be made in the study plan.

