## **17.0 Data Analysis, Management\* and Confidentiality**

**17.1** Data Management. All data will be entered into REDCap (supported by both Emory and CHOA), a secure web-based application for managing surveys and databases online, and exported into SPSS. The first step will be to compute descriptive statistics for all measures (means, standard deviations, range and skewness). This process will allow us to determine if there are any extreme outliers and whether the variables are normally distributed. If a variable is not normally distributed, log transformations will be used in all further analyses. Bivariate correlations among demographic variables and variables of interest will be examined to identify any meaningful covariates that will need to be controlled in further analyses. Missing data will be handled by using Multiple Imputation or Maximum Likelihood methods of handling missing data.

**17.2** Treatment Feasibility. Feasibility will be assessed using 4 metrics:

- 1) Study recruitment and enrollment statistics, such as proportion of eligible participants approached for the study who consent to participate
- 2) Treatment adherence as demonstrated by drop out rate, session completion, missed/rescheduled treatment sessions, therapist ratings of participants' homework completion, including the proportion of participants who attend at least 80% of sessions
- 3) Proportion of participants who complete study assessments
- 4) Participant ratings on whether they thought the Back2Life program is a reasonable approach for chronic pain management, if the program was helpful, could be integrated into their lifestyle, and description of barriers in implementing the program.

**17.3** Treatment Acceptability. Acceptability of the intervention will be assessed through the Treatment Evaluation Inventory Short Form as well as qualitative interviews that will elicit perceptions about treatment content (utility, appropriateness) and format (convenience, number and length of sessions). See Appendix B for Interview Guide. Audio recordings of qualitative interviews will be transcribed for analysis. A coding system for thematic domains

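### Hypothesis 2 is worded for completers while the rest of the plan points to all 25 enrolled; with follow-up after stopping left optional or unaddressed, the single-arm effect and the 30% responder rate can be biased

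*Combined protocol and SAP*

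**What the plan says.** **Who is in the efficacy claim.** Hypothesis 2 (2.3) reads "Participants who complete the Back2Life treatment program will report reductions in pain interference and pain symptoms", the latter meaning intensity and frequency, at post-treatment and at 6 months. It continues "Preliminary efficacy will be defined as clinically significant" reductions of at least 30% in pain interference and pain. The document does not say what completing the program means. It could be the 6 standard sessions or all of the 6 to 10 assigned. The 80% attendance threshold in 2.2 and 17.2 is a feasibility measure and is not tied to Hypothesis 2.

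**Who is in the analysis.** Section 2.1 gives n=25 and 17.5 bases power on n=25. Section 17.1 says "Missing data will be handled by using Multiple Imputation or Maximum Likelihood methods of handling missing data". Section 17.4 lists effect sizes with 95% intervals, repeated measures ANOVA, paired or Wilcoxon tests and individual reductions of at least 30%. It names no analysis set, no denominator and no rule for a missing follow-up.

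**Who is followed after stopping.**
- Under 14.1, if a participant chooses to go off treatment or leave the study, "participants may be asked to have some final study procedures completed". The examples given are surveys at the planned end of the program and at 3 and 6 months.
- Under 14.2, "Study personnel may stop participant involvement in the study without participant consent for any reason to maintain the best interest of the participant". No later assessment is mentioned.
- Section 6.5 places the post-treatment survey "after completing the standard 6-session program (post-treatment evaluation"). It also says that all teens and parents do the 3- and 6-month assessments.

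**Design.** Section 1.0 describes a "Single-Arm, Uncontrolled Behavioral Clinical Trial".

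**The concern.** Sections 2.3 and 17.1 imply different populations. Imputation or maximum likelihood has a purpose only if teens with missing outcomes stay in the analysis, whereas a completer hypothesis leaves out those who stopped. Nothing in 17.4 settles which one governs, so the analysis set could be chosen after the results are seen.

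The follow-up wording makes this harder to repair later. A teen who stops at session 3 has no date for the post-treatment survey under 6.5 and only a possible request under 14.1. A teen stopped by staff has no stated follow-up. If teens stop because pain worsens or the program is not helping, their outcomes are the ones most likely to be missing. Imputation would then rest on an assumption about missingness that the plan does not state.

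A single-arm trial has no control group to show selective retention, so it would pass straight into the effect size and the responder share. Section 5.0 uses the result to decide whether the program goes on to a randomized trial. Section 3.2 names poor engagement as a weakness of earlier cognitive-behavioral trials in sickle cell pain, so some non-completion is foreseeable.

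**Working it through.** **Inputs.** From the documents: n = 25 (2.1, 17.5), d = 0.55 and power of about 80% (17.5). Not given, so assumed: two-sided 5% level (in line with the 95% intervals in 17.4), the drop-out rate, and how far staying in the program is related to improvement.

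**1. The plan's own power figure.** Treat d as the standardized mean change:

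power = Φ(d√n − 1.96) = Φ(0.55 × 5 − 1.96) = Φ(0.79) = 78.5%.

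This reproduces the stated figure; the exact t calculation gives 75.1%. Either way all 25 teens need paired data. With pairs from only 20, power is 69.1% (normal) or 64.6% (t). So 17.5 is a calculation for all enrolled teens, not for completers.

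**2. Responder rate.** Let m teens complete, with R responders among them. The completer rate is R/m. The all-enrolled rate lies between R/25 (no non-completer responds) and (R + 25 − m)/25 (all do). With m = 20 and R = 10:
- completers: 10/20 = 50% (exact 95% interval 27% to 73%);
- all enrolled: from 10/25 = 40% to 15/25 = 60%.

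The largest possible overstatement is a factor of 25/m: 1.25 at m = 20 and 1.67 at m = 15.

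**3. Mean change.** Suppose completers show 0.55 SD and 20% do not complete. The all-enrolled mean is 0.8 × 0.55 + 0.2 × x, where x is the non-completers' change:
- x = 0 gives 0.44;
- x = 0.275 gives 0.495;
- x = 0.55 gives 0.55, with no bias.

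**4. Selective retention.** In simulated trials of 25, change = μ + r·z + noise (total SD 1). Teens with the highest z stay, and the others are left out entirely, with no follow-up and no imputation. The mean z of those who stay is 0.337 when 20 of 25 stay (20% drop-out) and 0.452 when 18 of 25 stay (28%). The mean change among stayers is therefore μ + r × 0.337 or μ + r × 0.452.

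| Stay | r | Mean observed d, μ = 0 | Significant improvement, μ = 0 | Mean change (original SD units), μ = 0.55 |
|---|---|---|---|---|
| 20 | 0.3 | 0.11 | 7% | 0.55 + 0.10 = 0.65 |
| 20 | 0.5 | 0.19 | 12% | 0.55 + 0.17 = 0.72 |
| 18 | 0.3 | 0.15 | 8% | 0.55 + 0.14 = 0.69 |
| 18 | 0.5 | 0.25 | 17% | 0.55 + 0.23 = 0.78 |

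Without selection, significant improvement under μ = 0 would be 2.5%. For μ = 0.55 the table gives mean change rather than observed d, because small-sample bias alone lifts the average d to 0.57 or 0.58 with no selection at all.

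**The case against.** A reader might infer three stronger things, and the documents support none of them.

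- *That efficacy will be analysed only in completers.* The restriction is in the wording of the hypothesis. Section 17.4 does not repeat it, 2.1 and 17.5 work with 25, and 17.1 plans to retain cases with missing data.
- *That teens who stop are not followed.* Section 14.1 foresees surveys at the planned end of the program and at 3 and 6 months, and 6.5 has all teens assessed at 3 and 6 months. The weakness in 14.1 is that the request is discretionary. Only 14.2 is silent, and nothing indicates how often staff-initiated stops would occur.
- *That the estimates are inflated.* Neither the size nor the direction is shown. It depends on outcomes in those who stop, and stoppers who did well would push the bias the other way.

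The plan has further points in its favour. Section 5.0 describes a proof of concept in a select sample under optimum conditions, which a completer hypothesis fits. Section 17.5 calls the efficacy analysis exploratory. Section 17.2 reports drop-out, session completion and assessment completion, so readers will see attrition. Between-session diaries (6.4) and medical-record data (6.13) could inform an imputation model, although they do not replace the questionnaires.

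These points limit the claim but do not remove it. Preliminary efficacy is part of the Primary Aim and the primary endpoints (4.1), the population remains unresolved between 2.3 and 17.1, and 17.1 is not linked to the paired tests or the responder count.

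**Conclusion.** The point holds as an unresolved analysis population combined with follow-up that is not secured after stopping. In this single-arm design the consequence is a possible upward bias, and its size rests on assumptions because the documents give no drop-out rate. At 20% non-completion, a completer-based result overstates the all-enrolled result by anything from nothing (non-completers change equally) to a factor of 1.25 (non-completers unchanged, or none responding). The simulated range of d from 0.11 to 0.25 with no true effect also depends on the assumed correlation and on stoppers being omitted altogether. Sections 6.5, 14.1 and 17.1 would lessen that if carried out, so the range shows what is at stake and does not forecast this trial's result. The change has to be made prospectively, because surveys not requested at the time cannot be recovered.

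**What to change.** 1. **Analysis set (2.3, 17.4).** Name every enrolled teen with a baseline assessment as the main efficacy set, whatever the number of sessions attended, analysed with the missing-data methods of 17.1. State which method applies to the ANOVA, the paired comparisons and the responder count. Define completion and label the completer analysis as supportive.
2. **Follow-up (14.1, 14.2).** Separate stopping sessions from withdrawing permission for data collection. State that every teen who stops sessions, by their own or a staff decision, will be asked for the remaining surveys and diary at the scheduled dates unless that permission is withdrawn. This concerns data collection only, not when sessions should stop. Reconcile the timing of the 3- and 6-month surveys, which 14.1 counts from the end of the program and 6.5 counts from baseline.
3. **Responder rate (17.4).** Report the reduction of at least 30% over all enrolled teens, with imputed and observed-case figures side by side. Add a sensitivity bound that counts missing outcomes as not achieved. That bound is itself an assumption and should not replace the imputed figure.

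**Cost.** Protocol wording and a few extra survey requests, using the remote routes in 6.5 and the per-visit payments in 6.15. The efficacy estimate will probably be less favourable.

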## **5.0 Study Intervention / Design**

*A proof-of-concept trial is a cost-effective method to determine if the treatment package can achieve a clinically significant improvement in outcome in a small, select sample. As a single-arm trial, a proof-of-concept determines whether the treatment merits rigorous and costly testing using an RCT or requires further optimization, thereby minimizing waste of resources and first ensuring clinically significant improvements can be achieved under optimum conditions.*

*A manualized treatment protocol, including intervention content, delivery style, and materials were adapted for optimization based on analyses of qualitative feedback from qualitative interviews and theater testing (i.e., pre-testing the intervention with the target audience to examine attitudes towards the format, content, etc). The treatment program includes 6-sessions of standard treatment (delivered to all participants) and 1-4 tailored sessions to address common co-morbidities associated with chronic pain (sessions assigned based on results of baseline assessment). The treatment manual leverages existing evidence-based interventions into a treatment package that will be tailored to individual patient and family needs.*

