and a coding scheme will be developed. Qualitative data will be analyzed using MAXQDA. Interview data will be coded by two independent reviewers to enhance confirmability and dependability of conceptual domains. Describe the steps that will be taken to secure the data (e.g., training, authorization of access, password protection, encryption, physical controls, certificates of confidentiality, and separation of identifiers and data) during storage, use, and transmission.

**17.4** Preliminary efficacy will be examined by calculating standard effect sizes and 95% confidence intervals on primary outcomes (pain interference, pain, coping) at post-treatment and 3- and 6-month follow-up. Changes in primary outcomes over time will be assessed using repeated measures ANOVA. Comparisons between time points will be made using paired tests or Wilcoxon tests. In an adjusted analysis, potential control covariates (e.g., child age, number of sessions, changes in treatment) will be examined as appropriate. Based on past CBT pain trials, pain reductions typically occur from baseline to follow-up and independent of changes in pain interference. To account for potential non-significant changes in pain intensity, we will examine individual clinically significant ( $\geq 30\%$ ) reductions in pain and interference.

**17.5** Power Analysis: We are not attempting to fully power this proof-of-concept study and will only examine preliminary efficacy using exploratory analyses. Preliminary power analyses were based on meta-analysis of CBT for pediatric chronic pain. We estimate an effect size of  $d=.55$  for pain reduction at follow-up (30% pain reduction). A sample size of  $n=25$  would achieve power estimates of approximately 80%.

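### The 30% improvement rule for pain interference depends on a PROMIS score metric that the plan does not state, and the only support for 30% concerns pain

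*Combined protocol and SAP*

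**What the plan says.** - Section 2.3 (Hypothesis 2): "Preliminary efficacy will be defined as clinically significant" reductions of 30% or more in pain interference and pain. It does not say whether this refers to a group mean or to individuals.
- Section 17.4 applies the cut to individuals, for both pain and interference: "To account for potential non-significant changes in pain intensity, we will examine individual clinically significant" reductions. The same section plans standardised effect sizes with 95% confidence intervals, repeated measures ANOVA, and paired or Wilcoxon tests.
- Section 6.12 lists interference first among the primary treatment outcomes. It names an 8-item PROMIS Pediatric short form, by self-report and parent proxy, but gives no score range, item coding or T-score conversion.
- Section 6.14 contains the only PROMIS metric in the document: a T-score cut of 65, on the depressive symptoms form.
- Section 17.5 contains the only support for 30%. It takes d=.55 "for pain reduction at follow-up (30% pain reduction"), with power of about 80% at n=25.
- Section 5.0 says a proof-of-concept trial serves to "determine if the treatment package can achieve a clinically significant improvement in outcome in a small, select sample", and that "a proof-of-concept determines whether the treatment merits rigorous and costly testing using an RCT or requires further optimization".

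**The concern.** A percent reduction has a fixed meaning only when the score has a true zero. Pain days per month do. A T-score does not, and a raw questionnaire sum has a zero only if its items are coded from zero. Until the interference metric is written down, one child's questionnaires can meet or miss the 30% cut according to how they are scored.

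The threshold also lacks a stated basis for this outcome. Section 17.5 ties 30% to pain. Section 3.2 mentions lower pain-related disability after CBT but attaches no percentage to it.

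At stake is how the trial answers its own question. For interference, 30% is the only meaning the protocol gives to clinically significant improvement, which section 5.0 makes the purpose of a proof-of-concept trial. A treatment that improves interference by as much as the plan hopes to see for pain could still miss the definition in section 2.3.

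**Working it through.** **Inputs from the protocol.** The 30% cut (2.3, 17.4); 8 items (6.12); d=.55, n=25 and power of about 80% (17.5); at least 12 pain days per month for eligibility (10.1).

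**Assumptions, because the protocol is silent.** T-score mean 50 and SD 10; baseline interference T from 50 to 70; five response options per item, coded 0-4 or 1-5; two-sided alpha 0.05. The T-score and raw-sum cases below are alternatives and do not add up.

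**1. The plan's own figure.** For a paired comparison, the noncentrality is d × √n = 0.55 × 5 = 2.75. The normal approximation gives Φ(2.75 − 1.96) = 78.5%, which agrees with about 80%. The noncentral t gives 75.1%. So d=.55 reads naturally as the planned pre-post effect, and section 17.5 attaches it to pain.

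**2. What pairing d=.55 with 30% implies.** If d is scaled on the score SD (the standardiser is not stated), 0.30 × mean = 0.55 × SD, so SD/mean = 0.30/0.55 = 0.55. On the assumed T-score, SD/mean runs from 10/70 = 0.14 to 10/50 = 0.20. The pairing cannot carry over to that metric.

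**3. If interference is a T-score.**

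| Baseline T | 30% drop (points) | In SD | End score | 5.5 points as % of baseline |
|---|---|---|---|---|
| 50 | 15.0 | 1.50 | 35.0 | 11.0% |
| 60 | 18.0 | 1.80 | 42.0 | 9.2% |
| 65 | 19.5 | 1.95 | 45.5 | 8.5% |
| 70 | 21.0 | 2.10 | 49.0 | 7.9% |

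The last column is 0.55 × 10 = 5.5 points. The required drop is 1.5/0.55 = 2.7 to 2.1/0.55 = 3.8 times that effect. Ending at or above 50 after a 30% drop needs a baseline of at least 50/0.7 = 71.4.

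Scaling d on the SD of change does not close the gap. With equal SDs and pre-post correlation r, the SD of change is 10√(2(1−r)), which is 14.1 at r=0 and 7.7 at r=0.7. Then 0.55 SD is 7.8 or 4.3 points, still well under 15.

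As an illustration and not a forecast, suppose a mean drop of 5.5 points and normal change with SD 7.7 to 10. The share reaching 30% is 1 − Φ((0.3T − 5.5)/SD). It runs from 3.5% (T=65, SD 7.7) to 17.1% (T=50, SD 10).

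**4. If interference is a raw sum.** Coding 1-5 adds 8 to every total, so the points needed rise by 0.3 × 8 = 2.4 at every baseline. With identical answers:
- 0-4 coding: 20 to 14, 6/20 = 30.0%, meets the cut.
- 1-5 coding: 28 to 22, 6/28 = 21.4%, does not.

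**5. A measure where 30% is well defined.** Pain days per month have a true zero. A 30% reduction is 3.6 of 12 days, or 9 of 30.

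**The case against.** The strongest case on the other side is that little turns on this. The effect sizes, confidence intervals, ANOVA and paired or Wilcoxon tests never use the 30% cut. Section 17.4 brings in the individual analysis as a supplement, section 17.5 says the study "will only examine preliminary efficacy using exploratory analyses", and no responder target or go/no-go rule uses the count. All of that stands and limits the weight of the point. It does not remove it, because section 2.3 makes the cut the definition of preliminary efficacy.

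It can also be said that the short form is a named, cited instrument and that section 25.2 provides standardised training in scoring. That is fair: the protocol shows that the scoring is not written down, not that it is a free choice. Naming T-scores as the metric would still leave the rule facing the figures in step 3.

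Three stronger readings are tempting, and the documents do not support them:

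- A reader might infer that 30% is simply too strict. That needs T-scores, which are only inferred from the depression cut in section 6.14. The protocol also gives no baseline interference score and no minimal important change to judge strictness by.
- A reader might infer that the rule is flawed because it asks more of children who start worse. Every percentage rule does so. Pain days go from 3.6 to 9, a 2.5-fold rise, against 1.4-fold for 15 to 21 T-score points.
- A reader might take the remark in section 17.4 that "pain reductions typically occur from baseline to follow-up and independent of changes in pain interference" as evidence against a shared threshold. It says whether the two outcomes move together and has no bearing on whether 30% suits either.

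**Conclusion.** The point holds in a conditional form. It is certain from the text that 30% is applied to interference, that the interference metric is not stated, and that the only support for 30% concerns pain. It follows that meeting the cut on interference depends on the scoring.

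The size depends on assumptions. Under T-scores, the likelier reading but not a stated one, the rule needs 15 to 21 points where a 0.55 SD improvement gives 5.5. The treatment could then show on interference the effect size planned for pain and still miss the definition in section 2.3. Under raw sums, the bar moves by 2.4 points with the item coding.

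This is worth correcting before analysis. It does not undermine the main efficacy estimates, and a reader should not infer that the trial's conclusion hangs on the responder count.

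**What to change.** Before analysis:

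1. State in section 6.12 the score metric for PROMIS pain interference.
2. If that is a T-score, or any score without a true zero, replace the 30% rule for interference in sections 2.3 and 17.4 with a prespecified absolute change on that metric, justified by the sponsor.
3. If it is a raw sum, fix the item coding and justify whatever threshold is kept.
4. Keep 30% for measures with a true zero, such as pain days per month.

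The cost is wording in sections 2.3, 6.12 and 17.4, with no new data. The downside is two responder definitions in place of one. Settling the metric in advance also removes any chance of choosing the scoring after seeing the results.
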